Participants were assessed at the end of each treatment session for adverse events (AEs), vital signs, and discomfort ratings (for potential scalp sensations associated with CB-tACS) using the commonly used questionnaire in CB-tACS trials, with telephone call every 2 weeks to record AEs during follow-up. Participants were instructed to report any additional adverse

events experienced during or after treatment that were not included in the questionnaire.

Outcomes

Primary outcome measurement

Efficacy outcome. The primary outcome measurement was the proportion of participates with clinical remission at the completion of treatment (defined as the reduction of SARA score at least 1.5 point from baseline).

The secondary outcome measures were proportion of patients with clinical remission at T2 and T3, and the changes at different timepoints (T1, T2, T3) from T0, compared to sham stimulation, including SARA, ICARS, EQ-5D, and gait variability. The safety outcomes included vital signs (blood pressure, body temperature, heart rate, pulse), adverse effects linked to tACS.

Data management And Quality Control

To ensure the rigor of this study, the whole process will be carried out strictly according to Guidelines for Good Clinical Practice of the International Conference on Harmonisation (ICH). Data will be collected from T0, T1, T2, and T3, respectively. All investigators, trial supervisors, and raters involved in the study must be trained before they participate in communicating and instructing participants, assessing, collecting data, and completing the CRF. Double entries of data into the software Yidu Research platform (Yiducloud (Beijing) Technology Ltd.) will be finished by two independent investigators, and these electronic data will be stored on a secure university server with regularly back-up and password protection. Yidu Research platform has an authority management mechanism associated with personnel and roles and a strict data audit mechanism to fully protect the security of data utilisation. Double-check will be performed to correct inconsistent entries or typos. The details of the quit participants, including reasons, date, AEs, and duration of the treatment, will be recorded. The final trial dataset, including the intent-to-treat and per-protocol dataset will be analyzed by an independent statistician.

Data analysis

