Design: A triple-blind, randomized sham-controlled trial with two groups. At least 84 subjects will be recruited and randomized into either active tACS group or sham tACS group. Interventions: Cerebellar tACS (40 min, 2 mA, ramp-up and down periods of 10s each) will be delivered over 10 sessions, distributed in two groups of five consecutive days with a two-day break in between. The active tACS group will receive whole course current stimulation, while the control group will receive a daily 40–seconds current stimulation for two weeks. Primary outcomes: The primary outcome was the difference in total Unified Multiple System Atrophy Rating Scale (UMSARS) score between the two groups being treated for 2 weeks (T1). Secondary outcomes: The difference in total UMSARS score between the two groups at 1month follow-up visits (T2) and 3-month follow-up visits (T3). Ataxia symptoms measured by SARA and The International Cooperative Ataxia Rating Scale (ICARS); health–related quality of life (HRQoL) measured by the the Multiple System Atrophy Quality of Life questionnaires (MSA-QoL); and objective quantitative outcome for gait measured by the wearable sensors.

Impact of the project: With the promising preliminary benefits of tACS on improving cerebellar motor functions and is safe and effective in treating neurological diseases, however, the efficacy of tACS in cerebellar disorders with MSA-C has not been clinically investigated. Therefore, we performed a triple-blind, parallel-group, sham-controlled, randomized clinical trial to investigate the efficacy and safety of tACS in a large cohort of patients with MSA-C. The primary outcome assessed ataxia severity, and secondary outcomes evaluated quality of life, and adverse events (AEs).

Introduction

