Our sample size was calculated as previously described (PMID: 31278067). This study is expected to produce α of 0.05 at 80% power for a treatment effect of 50% on the annual progression of the movement examination score on the Unified Multiple System Atrophy Rating Scale (UMSARS); this contains 4 points from the active group and 8 points from the placebo group, which is above the minimal clinically detectable significant level of 3.8 points (PMID: 27474888). Therefore, we conducted this study to determine whether active tACS treatment would have a positive effect on MSA-C patients. The target total patients was 84, with an expected attrition rate of 10%. Transcranial alternating current stimulation intervention

We applied 3 saline-soaked (0.9% NaCl) surface sponge electrodes (all rectangular-shaped in two sizes of 5×5 and 5×7 cm) to the scalp and used the battery-driven current stimulator (Neustim NSS18, Neuracle, Changzhou, China) to administer tACS. Five-digit codes were used to ensure blinding of the study coordinators with regard to the stimulation conditions. The Neustim NSS18 device does not display any information that would provide insights into whether active or sham stimulation is applied. The return electrode (5×7 cm) was placed 2 cm below the inion and the two active electrodes were over the bilateral buccinator muscles. After computational modeling of electric field distribution, we chose this CB-tACS particular montage with an extracephalic electrode, which can lead to significant entrainment of brain oscillations ⁶. Electrodes are fixed with elastic gauze and coated with conductive gel to reduce contact resistance (<5 k Ω for all sessions).

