and then continue walking until I tell you to stop. Walk at your normal speed, as if you were walking down the street to go to the store." Gait parameters were measured using two ninedimensional (three-axis accelerometers + three-axis gyroscopes + three-axis magnetometers) Inertial Measurement Unit (BWT901CL, WIT-MOTION, Shenzhen, China), as well as two flexible pressure sensor insoles. Use Visual Studio software (Visual Studio 2017, Microsoft, the USA) was used to synchronize timestamp and task data and to process the raw data. Participants completed the walk three times at their selected speed and the mean and standard deviation of gait parameters, including stride time variability, double support time variability, toe-out angle variability, and toe-off angle variability were determined. A detailed description of the technical devices is provided elsewhere. ³⁹

Adverse Events

Participants were assessed at the end of each treatment session for adverse events (AEs), vital signs, and discomfort ratings (for potential scalp sensations associated with CB-tACS) using the commonly used questionnaire in CB-tACS trials, with telephone call every 2 weeks to record AEs during follow-up. Participants were instructed to report any additional adverse events experienced during or after treatment that were not included in the questionnaire.

Outcomes

Primary outcome measurement

The primary outcome was the change from baseline to week 2 in the Unified Multiple System Atrophy Rating Scale (UMSARS) total score (sum of parts I and II). PMID: 15452868. Higher UMSARS scores denote poorer health.

The secondary outcomes included the change in UMSARS part II (UMSARS II; motor examination scores, on which scores range from 0 to 56), the changes at different timepoints (T1, T2, T3) from T0, compared to sham stimulation, including SARA, ICARS, MSA-QoL, and gait variability. The safety outcomes included vital signs (blood pressure, body temperature, heart rate, pulse), adverse effects linked to tACS.

Data management And Quality Control

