Per-protocol (PP) refers to the set of cases that have completed the overall study protocol, a subset of the FAS in which each subject in the dataset is a valid case or sample with good adherence, no protocol violations, and complete baseline values for key indicators. Missing data

Due to the long duration of intervention and the long follow-up period, so there may be a lot of missing data. If missing data were found, the percentage of missing data will be reported, the potential patterns of missing data should be examined, and appropriate method should be used for multiple imputation of missing data. The multiple imputation method will be preferred for analyzing the missing data, and the complete-case data should be reported in the manuscript as sensitivity analysis.

Analysis of primary outcome

The Type I error rate (α -level) used in the assessment of χ^2 analysis or Fisher's Exact test for the primary efficacy outcome is 5%. The assessment of significance for the A-tACS versus StACS contrasts will use χ^2 analysis or Fisher's Exact test, based on ITT, PP, and sensitivity analysis (multiple assumptions for the missing value).

Analysis of secondary outcomes

The Type I error rate (α-level) used in the assessment of pair-wise treatment comparisons for the primary efficacy outcome is 5%. All secondary outcomes will be compared between groups on the basis of intention–to–treat (ITT) principle. GEE models will be used to assess differential change of each secondary outcomes across different time–points between two groups and within group from baseline.

ALFF, ReHo, and FC Analysis

Statistical analysis of MRI data was performed using Matlab2013b, SPM12

(https://www.filion.ucl.ac.uk/spm/) (Sidhu et al. 2016). The Flexible factorial of second-order analysis was used to design the statistical matrix and to set the three factors of subjects, groups, and time. Groups and time were fixed factors, and the serial number of subjects was a random factor. Then, the interaction matrix of groups × time to analysis was set to determine the intergroup interaction effect. The resulting statistical map was set at p<0.05 (AlphaSim correction) with a combined voxel p<0.001. Use RestPlus toolbox

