(https://github.com/topics/restplus, version 1.2) was used to extract the values of the above abnormal brain regions, and Bonferroni tests were performed for all results with significant differences to verify between-group differences. Statistical significance was set at p<0.05. Image presentation used the xjview toolbox in Matlab 2013b.

Analysis of intra-network functional connectivity

A one-sample Student's t-test was applied to the spatial maps of all participants for each IC using the SPM12 toolbox, and regions surviving multiple comparison corrections with voxel-level family-wise error (FWE) correction (p<0.05) were saved as the specific group-level mask for each group. These four masks for each IC were then integrated into a union mask, which was used for the group comparison. A single model using a flexible-factorial design (2×2) was performed to obtain the ICs showing significant between-group differences. Regions showing significant differences (voxel-level FWE correction, p<0.05) were saved as the mask for subsequent post-hoc analyses, and the significance level was set at p<0.0125 (0.05/4) for Bonferroni correction across 4 tests.

Software and significant level of the statistical analyses

IBM SPSS 26.0 (IBM, Armonk, NY, USA) software and R, version 4.2.1 software (The R Project for Statistical Computing, www.r-project.org) will be used for all statistical analysis. Statistical significance was defined as P <0.05 with 2-sided testing.

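### The MSA-C protocol assigns a χ²/Fisher test to a primary outcome that is a numeric change in UMSARS total, and defines no responder category

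*Protocol*

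**What the plan says.** The MSA-C protocol describes its primary outcome as a score in three places.

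- The Procedures and Outcomes sections: "The primary outcome was the change from baseline to week 2 in the Unified Multiple System Atrophy Rating Scale (UMSARS) total score". The Outcomes section adds that the total is the sum of parts I and II.
- The abstract: "The primary outcome was the difference in total Unified Multiple System Atrophy Rating Scale (UMSARS) score between the two groups being treated for 2 weeks".

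None of these gives a threshold for response.

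The MSA-C section headed Analysis of primary outcome names one kind of test. The active versus sham "contrasts will use χ^2 analysis or Fisher's Exact test", in the ITT, per-protocol and sensitivity analyses alike, and the 5% error rate is attached to that same test.

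GEE appears in the MSA-C protocol for two purposes: adjustment for baseline differences (Data analysis) and the secondary outcomes (Analysis of secondary outcomes).

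The SCA3 protocol has the same primary-analysis paragraph, but its outcome is binary: "The primary outcome measurement was the proportion of participates with clinical remission at the completion of treatment", with remission defined as a SARA reduction of at least 1.5 points.

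**The concern.** A χ² or Fisher test compares how patients are distributed over categories. A change in UMSARS total is a number of points, so the test has nothing to work on until someone divides the scale. The protocol does not say where to divide it, or that it should be divided at all.

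Three things are at stake, all on the confirmatory test:

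- **Choice of cut-point.** It is left open. Nothing in the protocol prevents it from being chosen after the data are seen.
- **Power.** Dichotomising a continuous score discards information.
- **Estimate.** A contingency-table test gives no estimate of the UMSARS difference, which is the quantity the trial set out to measure.

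An analyst who does the sensible thing and compares means departs from the protocol on its primary test.

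**Working it through.** **1. Outcome and test side by side**

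| | SCA3 protocol | MSA-C protocol |
|---|---|---|
| Primary outcome | Proportion with SARA reduction ≥ 1.5 points | Change in UMSARS total (I+II) at week 2 |
| Type | Binary | Numeric |
| Sample size based on | 25% vs 60% | 4 vs 8 points |
| Test named | χ² or Fisher | χ² or Fisher |

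Only the last row fails to change with the outcome.

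**2. Do the sample-size inputs fit the test?**

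*SCA3.* Two proportions, 0.25 and 0.60, two-sided 5%, 80% power: the usual formula gives 31 per arm, or 36 with continuity correction. Then 36/0.90 = 40 per arm. This reproduces the stated 36 and 40, so the SCA3 design and test agree.

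*MSA-C.* The protocol states "This study is expected to produce α of 0.05 at 80% power", with a 4-point difference, a total of 84 and 10% attrition. No proportions are given, so a χ² design has no inputs. No SD is given either, so 84 cannot be reproduced; one can only solve for the SD that fits:

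- Evaluable per arm: 84 × 0.90 / 2 = 37.8, taken as 38.
- SD = 4 / [(1.960 + 0.842) × √(2/38)] = 4 / 0.643 = 6.2.
- With all 42 per arm evaluable, the same formula gives 6.5.

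The MSA-C sample size is therefore that of a comparison of means.

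**3. What a dichotomised analysis would cost**

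This is an illustration. Assume normal change scores, SD 6.2, 38 per arm and a true difference of 4/6.2 = 0.645 SD.

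- *Comparison of means:* power about 80% by construction; 79.7% in 20,000 simulated trials.
- *Cut midway between the two means:* proportions Φ(−0.3226) = 0.3735 and 0.6265, difference 0.2530. Null SE = √(2 × 0.5 × 0.5/38) = 0.1147; alternative SE = √(2 × 0.3735 × 0.6265/38) = 0.1110. Power = Φ[(0.2530 − 1.96 × 0.1147)/0.1110] = Φ(0.25) = 60%. Simulation gave 60.7%.
- *Cut one SD away from that midpoint:* proportions 0.0930 and 0.2491, difference 0.1561; null SE 0.0864, alternative SE 0.0845. Power = Φ[(0.1561 − 1.96 × 0.0864)/0.0845] = Φ(−0.16) = 44%.
- *Split at the pooled sample median* (0.65 SD, 4,000 simulated trials): t-test 80.5%, χ² 58.1%, Fisher 58.1%. A repeat with 20,000 trials gave 79.4% and 56.9%. With scores rounded to integers, the split gave about 61% for uncorrected χ² and 53% for Fisher.

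The loss is about 20 points of power at a favourable cut-point and more at an extreme one.

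**The case against.** **A sentence may have been lost.** The general sentence on primary and secondary outcomes in the MSA-C Data analysis section is ungrammatical. Its SCA3 counterpart is the same except for a run that names the ITT comparison and GEE models. The run may have been dropped by the authors or in reading the PDF. If it was, the MSA-C plan also names GEE for the primary outcome, which is a workable method. This stands as a mitigating possibility, but it does not remove the error. The dedicated section would still name χ²/Fisher, and the protocol would then hold two conflicting primary analyses.

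**The test can be run.** A cut-point could be declared before unblinding, so a data-driven choice is invited but not forced. That is fair. The accurate statement is that the named test does not address the stated outcome and that no categorisation is defined.

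**The power figures are assumption-based.** They are. The SD is solved from the total of 84 and a 4-point difference, and the protocol gives that difference for annual progression of the movement examination, not for a two-week change in the total score. The figures show the relative cost of dichotomising, not the power of this trial. One could also cross-tabulate the raw change values (about 6% power in simulation), but no analyst would, so nothing here rests on that.

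**The analysis plan may settle it.** An SAP may supply detail that the protocol leaves open. Here the protocol states an unsuitable test, so an SAP could repair it only by contradicting it.

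**Conclusion.** The concern holds and must be fixed before the primary analysis. The mismatch is visible in the protocol text and depends on no assumption: a numeric primary outcome, no responder definition, and a test for proportions. That the paragraph was carried over from the SCA3 protocol is a likely explanation, but an inference.

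The size of the consequence does depend on assumptions. With 38 per arm, normal scores and an effect of about 0.65 SD, dichotomising near the centre lowers power from about 80% to between 53% and 61%, depending on the test version and the rounding of scores. A cut one SD off centre lowers it to about 44%. Whatever the SD, the test as written would give no estimate of the UMSARS difference.

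**What to change.** Replace the MSA-C text under Analysis of primary outcome with the following content:

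- **Estimand and model:** the active minus sham difference in UMSARS total (I+II) at T1, from a linear model (ANCOVA) with baseline UMSARS total as covariate. With baseline in the model, analysing the T1 score or the change gives the same treatment difference, so this also reconciles the abstract with the Outcomes section.
- **Reporting:** adjusted mean difference, 95% CI and two-sided p-value at 5%.
- **Analysis sets:** ITT decides; per-protocol and missing-data analyses are sensitivity analyses.
- **Deletion:** remove χ²/Fisher for this outcome.

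A T1 contrast from the GEE model already planned for the secondary outcomes would also be acceptable, provided one method is named as primary. Complete the broken sentence in the MSA-C Data analysis section so that it agrees with that choice.

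The cost is an amendment to wording in the protocol and, if there is one, the SAP. No new patients or data are needed. The change should be dated and made before unblinding.

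### The AlphaSim 5% for the ALFF/ReHo/FC group×time map holds only under Gaussian smoothness with a correct FWHM and may be modestly exceeded (low severity)

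*Protocol*

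**What the plan says.** The section *ALFF, ReHo, and FC Analysis* is the same in both protocols. The software is fixed: "Statistical analysis of MRI data was performed using Matlab2013b, SPM12". The model is a flexible factorial, in which "Groups and time were fixed factors, and the serial number of subjects was a random factor", and the group×time interaction is the contrast of interest. The threshold is: "The resulting statistical map was set at p<0.05 (AlphaSim correction) with a combined voxel p<0.001". Values are then extracted from the regions that pass, and Bonferroni tests are run on them to verify the difference between arms.

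The next section, *Analysis of intra-network functional connectivity*, uses another correction in SPM12: "Regions showing significant differences (voxel-level FWE correction, p<0.05) were saved as the mask for subsequent post-hoc analyses". For its post-hoc tests, "the significance level was set at p<0.0125 (0.05/4) for Bonferroni correction across 4 tests".

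The closing section on software and significance level adds: "Statistical significance was defined as P <0.05 with 2-sided testing". Under *Outcomes*, the MSA secondary measures are UMSARS part II and changes "compared to sham stimulation, including SARA, ICARS, MSA-QoL, and gait variability"; the SCA3 list has EQ-5D in place of MSA-QoL. Neither list contains an MRI measure. Allocation in both protocols is in permuted blocks of four (design paragraph after *Exclusion Criteria*).

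**The concern.** AlphaSim simulates white noise smoothed to a given FWHM, forms clusters at the voxel threshold, and takes as its minimum the cluster size that chance reaches in at most 5% of simulated maps. If the real correlation falls off more slowly than a Gaussian, chance clusters are larger than the simulation expects. The minimum is then too small, and the error goes in the liberal direction. An FWHM set too low acts the same way. ReHo is a neighbourhood measure and so adds smoothness of its own.

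The step after the threshold gives no protection. The extracted regions were selected by the group×time contrast in the same data, so testing the arm difference inside them repeats the selection. A chance cluster that passes AlphaSim would be expected to pass this test too. The cluster threshold is therefore the main barrier between a chance cluster and a reported effect of tACS on brain function.

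The point concerns the error rate within one map. How many maps are tested is a separate matter.

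**Working it through.** **Can the 5% be reproduced?** Not from the protocol, which gives no voxel size, mask, smoothing kernel, smoothness estimate or minimum cluster size. Such details may stand in an SAP or imaging manual, and their absence is not the complaint. The check therefore runs on assumed inputs. Only the 5% map level and the voxel p<0.001 come from the protocol. It does not say whether the voxel threshold is one- or two-sided, so one simulation uses each.

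**Method.**
1. Threshold: k* is the smallest k with P(largest cluster ≥ k) ≤ 0.05 in null fields with Gaussian correlation exp(−r²/4s²), where s = FWHM/√(8 ln 2).
2. Error: P(largest cluster ≥ k*) in null fields with a longer tail, a·exp(−r²/2b²) + (1−a)·exp(−r/c).

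**Simulation A.** Assumed: 3 mm voxels, mask of 67,104 voxels, FWHM 8 mm, two-sided |z|>3.29, 26-neighbour clusters, 2,500 fields per setting. Result: k* = 21, with error 4.2% under Gaussian correlation. With matched half-width and an exponential share of 20%, 40% and 50% (scale 12–15 mm), the error is 5.5%, 7.8% and 10.1%. The Monte Carlo SE at 5.5% is √(0.055×0.945/2,500) = 0.5 points, so that value alone is not distinguishable from 5%.

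**Simulation B.** Assumed: 3 mm voxels, mask of 69,984 voxels, one-sided z>3.09, 18-neighbour clusters, 1,200 fields per setting. The long-tailed field has b = 3.5 mm, with a = 0.8, c = 10 mm (mild) or a = 0.6, c = 11 mm (moderate), and is then smoothed. The Gaussian FWHM is matched on the correlation ρ between adjacent voxels: s = √(−3²/(4 ln ρ)).

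| Smoothing kernel, tail | Matched FWHM (mm) | AlphaSim k* | Error, Gaussian | Error, long tail | k needed for 5% under long tail |
|---|---|---|---|---|---|
| 6 mm, mild | 9.4 | 35 | 4.9% | 7.7% | 42 |
| 6 mm, moderate | 10.7 | 46 | 4.9% | 10.3% | 61 |
| 8 mm, mild | 11.5 | 54 | 5.0% | 6.9% | 62 |
| 8 mm, moderate | 13.2 | 69 | 4.8% | 9.8% | 93 |

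The SE of the long-tail column is 0.7 to 0.9 points; for example √(0.103×0.897/1,200) = 0.9.

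**Effect of the voxel threshold.** In unsmoothed long-tailed fields (1,000 per setting; mild, moderate and a heavy tail with a = 0.4, c = 13 mm), the error at voxel p<0.001 is 10.6%, 18.8% and 30.9%. At voxel p<0.01, which the protocol does not use, it is 23.3%, 59.7% and 75.1%. The strict threshold removes much of the inflation, but not all.

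**Would random-field cluster FWE in SPM12 cure it?** The standard cluster-extent formula, with V voxels in the mask and R = V/(FWHM/3)³, is:
- E(m) = R(4 ln 2)^1.5 (2π)^−2 (u²−1) e^(−u²/2)
- β = [Γ(2.5)·E(m)/(V·P(Z>u))]^(2/3)
- k = [−ln(p)/β]^1.5, with p = −ln(0.95)/E(m)

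For FWHM 9.4 mm and u = 3.09: R ≈ 2,275, E(m) ≈ 19.2, β ≈ 0.51, p ≈ 0.0027, so k ≈ 39.5, against 35 for AlphaSim. Over the four smoothed settings its error is 2.3–2.9% under Gaussian correlation and 4.6–7.4% under the long tail. In the unsmoothed fields it is 5.4–25.1% under the long tail. It is stricter than AlphaSim but rests on the same kind of smoothness model.

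**The case against.** The strongest reply is that nothing here is a demonstrated error. The protocol does not describe the correlation of its images. If it is Gaussian and the FWHM is right, the rule delivers 4–5%. The longer tails are assumed, the lowest inflated figure (5.5%) is within simulation error of 5%, and the voxel threshold is already strict. Voxel-level FWE and cluster-extent correction are also different inferences, with different sensitivity to diffuse effects, so using one for each imaging analysis is no contradiction. MRI is not a listed outcome. All of this stands, and it sets the severity.

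It does not remove the point. The protocol names the method and claims a corrected 5%, and that claim rests on a condition it does not support.

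A reader might go further in three ways that the documents do not bear out:
- **The 5% is not delivered.** This cannot be stated as fact without knowing the smoothness of these maps.
- **The error is 13% or 25%.** In simulation A it is 13.0% or 25.5% if an FWHM of 8 mm is entered when the truth is 9 or 10 mm. Nothing in the text indicates such an entry error. The 10.6–30.9% for unsmoothed fields is likewise conditional, since the protocol does not say whether the maps are smoothed.
- **SPM12 cluster-level FWE is a free and complete cure.** The working shows that it is not.

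**Conclusion.** The concern holds in conditional form. The 5% per-map error attached to AlphaSim depends on Gaussian spatial correlation and a correct FWHM. On assumed inputs (3 mm voxels; total smoothness of 8 mm in A, kernels of 6–8 mm in B) it is about 4–5% when those conditions hold. With a longer-tailed correlation it is roughly 5.5–10% at the protocol's voxel p<0.001. The direction is firm, because longer tails can only make AlphaSim liberal. The size depends on tail shapes that the documents do not give.

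Severity is low. A reader might infer that the trial's efficacy conclusions are affected. They are not: the primary outcomes are SARA remission and change in UMSARS total score, and no listed secondary or safety outcome uses the map. What is exposed is the exploratory claim that tACS changed regional brain function.

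**What to change.** In *ALFF, ReHo, and FC Analysis* of both protocols, replace the AlphaSim correction by one of the following.

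1. **Cluster-level FWE p<0.05 at the same voxel p<0.001, by permutation (preferred).** Form one post-minus-baseline map per participant and permute arm labels within the randomisation blocks of four. Use the distribution of the largest cluster as reference. Exactness under the randomisation requires the within-block restriction; free shuffling of labels would not follow the design. A complete block allows 6 arrangements, so 20 blocks (80 participants) or 21 blocks (84) leave ample permutations even with some maps missing. If MRI is taken at more than one follow-up visit, use one change map per visit.
2. **Voxel-level FWE p<0.05**, as the protocol already does in its intra-network analysis. It does not rely on the distribution of cluster sizes. It is less sensitive to diffuse effects, and it was not simulated here.

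Do not present SPM12 random-field cluster FWE as free of assumptions. If AlphaSim is kept as a secondary display, report its smoothness estimate, mask and minimum cluster size. Describe the later Bonferroni tests on extracted values as descriptive, not as verification.

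Cost: a sentence or two per protocol and some computing time, with no new data. Some small clusters may no longer pass. In the four smoothed long-tail settings the minimum cluster rises from 35–69 to 42–93 voxels, an increase of 15% (54 to 62) to 35% (69 to 93).
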